### 5.2. Data Sets Analysed and protocol deviations

#### Data sets analysed

There will be nine patient sets defined for this trial: the Screened patients Set (SPS), the Safety Set (SS), the All Randomized Set (ARS), the Extended Full Analysis Set 1 & 2, the Full Analysis Set (FAS) 1 & 2 and the Per-Protocol Set (PPS) 1 & 2:

- Screened Patients Set (SPS) will include all patients having signed the inform consent form
- Safety Set (SS) will include all patients having received at least one injection of Investigational Medicinal Product (IMP) regardless of the quantity
- All Randomized Set (ARS) will include all patients having performed at least one MRI exam.
- Extended\_FAS1 will include all patients who have both gadopiclenol pre contrast and paired images assessable
- Extended FAS2 will include all patients who have both gadopiclenol and gadobutrol paired images assessable
- Full Analysis Set (FAS) will include all patients who have a valid primary criterion assessment
  - FAS1 will include all patients who have both gadopiclenol pre contrast and paired images assessable for primary criteria 1 for at least one matching lesion for at least one off-site reader
  - FAS2 will include all patients who have both gadopiclenol and gadobutrol paired images assessable for primary criteria 2 for at least one matching lesion for at least one off-site reader
- Per-Protocol Set (PPS) will include all patients who have no major protocol deviations and a valid primary criterion assessment:
  - PPS1 will include all patients from the FAS1 who have no major protocol deviations for primary criteria 1

- o PPS2 will include all patients from the FAS2 who have no major protocol deviations for primary criteria 2

Analyses Sets	Safety Set	All Randomized Set	Extended Full Analysis Set		Full Analysis Set		Per Protocol Set	
			Extended FAS1	Extended FAS2	FAS1	FAS2	PPS1	PPS2
Demographics and Population characteristics	✓				✓	✓		
Compliance					✓	✓		
Efficacy evaluation : primary analysis of primary criteria 1					✓		✓	
Efficacy evaluation : primary analysis of primary criteria 2						✓		✓
Efficacy evaluation: secondary analysis of primary criteria 1			✓		✓			
Efficacy evaluation: secondary analysis of primary criteria 2		✓		✓		✓		
Efficacy evaluation: Secondary criteria		✓	✓	✓	✓	✓		
Safety evaluation	✓							

The use of the PPS in the non-inferiority analysis will maximize the opportunity for both contrast agent to show the efficacy under the intended scientific model of the protocol. Indeed, there is a risk that poor compliance in both contrast agent groups would lead to similar outcomes from the two contrast agent groups in the FAS.

#### Protocol deviations

As per International Conference on Harmonization (ICH) E3 guideline, a protocol deviation is any change, divergence or departure from the trial design or procedures defined in the protocol, with or without impact to the patient safety or the efficacy assessments.

Protocol deviations will be gathered from monitoring files, clinical database and external vendors of off-site data (imaging data, laboratory data, IWRS).

If the reason of deviations is related to the COVID pandemic then it will be indicated in the Statistical Review Meeting Minutes and the corresponding deviation presented apart

Protocol deviations will be split in major and non major deviations. A major deviation is defined as a deviation having an impact on the primary criteria 1 or primary criteria 2. The initial categorization is proposed in this document, the final categorization will be performed before breaking the blind. The decision will be duly described in the meeting minutes.

The deviations are listed in the table below:

Category	Description	Source	Status
Inclusion criteria not met/ Non inclusion criteria met	Inclusion criteria n°6 not met: Patient not having read the information or not having provided his/her consent to participate in writing by dating and signing the informed consent prior to any trial related procedure being conducted	Clinical data base	Major
	Non inclusion criteria n°1 met: Patients with known	Clinical data base	Major

Category	Description	Source	Status
	or suspected lesion(s) referred for contrast-enhanced MRI of CNS or of heart or for MR Angiography.		
	Non inclusion criteria n°6 met: Patient having received any contrast agent (MRI or CT) within 3 days prior to first trial product administration, or scheduled to receive any contrast agent during the course of the trial or within 24 hours after the second trial product administration	Clinical data base	Non major
	At least one inclusion criteria except n°6 not met	Clinical data base	Non major
	At least one non -inclusion criteria except n°1 and n°6 met	Clinical data base	Non major
	eGFR at visit 2 or visit 4 below 30 mL/min/1.73m  and contrast agent administration performed	Clinical data base	Non major
	eGFR not measured within one day before contrast agent administration	Clinical data base	Non major
	eGFR measurement at visit 2 or visit 4 is missing	Clinical data base	Non major
	No pregnancy test done within 1 day before contrast agent administration for female of childbearing potential	Clinical data base	Non major
	Result of pregnancy test positive and contrast agent administration performed	Clinical data base	Non major
Trial disease	Procedure used for detecting the trial disease is not provided	Clinical data base	Non major
	Procedure used for detecting the trial disease is not adequate	Clinical data base	Non major
	Procedure used for detecting the trial disease is not performed within 12 months prior to ICF signature	Clinical data base	Non major
Imaging	Not matching lesion: among patients with gadopiclenol MRI examination available, those with no matching enhancing lesions on paired and pre contrast images for all off-site readers	Imaging data base	Major criteria1
	Not matching lesion: among patients with both MRI examinations available, those with no matching enhancing lesions at both examination for all off-site readers	Imaging data base	Major criteria2
	Imaging protocol not respected with major impact on co-primary criteria for gadopiclenol administration	Monitoring	Major
	Imaging protocol not respected with major impact on co-primary criteria for gadobutrol administration	Monitoring	Major criteria2
	Imaging protocol not respected with non-major impact on primary criterion	Monitoring	Non major
	Deviation to blind charter in regards to data correction	Monitoring	Non major
Unblinding	Blind not maintained on site	Monitoring	Non major

CONFIDENTIAL	STATISTICAL ANALYSIS PLAN PHASE III TRIAL GDX-44-011 VERSION NO. 2.0 DATED 25 JANUARY 2021	████████
		Page 23 / 57

Category	Description	Source	Status
	Blind not maintained at central reading level	Monitoring	Major
Forbidden concomitant medication	Concomitant medication or medical procedure taken between the two MRI significantly impacting lesion size and its enhancement pattern	Clinical data base	Major criteria2
	Patient having received any MRI contrast agent from 3 days prior to first trial product administration, until 24 hours after the second trial product administration	Clinical data base	Major
	Patient having received any CT contrast agent from 3 days prior to first trial product administration, until 24 hours after the second trial product administration	Clinical data base	Non major
IMP deviation	Patient does not receive the IMP allocated by randomization	Clinical data base and IWRS data base	Major
	Patient does not receive the kit allocated by IWRS	Clinical data base and IWRS data base	Non major
	Patient having performed MRI examination but not administered with gadopiclenol	Clinical data base	Major
	Patient having performed MRI examination but not administered with gadobutrol	Clinical data base	Major criteria2
	The gadopiclenol volume actually administered is different from the theoretical one from 10 to 20%	Clinical data base and IWRS data base	Non major
	The gadobutrol volume actually administered is different from the theoretical one from 10 to 20%	Clinical data base and IWRS data base	Non major
	The gadopiclenol volume actually administered is different from the theoretical one more than 20%	Clinical data base and IWRS	Major
	The gadobutrol volume actually administered is different from the theoretical one more than 20%	Clinical data base and IWRS	Major criteria2
	Temperature excursion for IMP	Monitoring	Non major
	Temperature excursion for gadopiclenol with risk of freezing	Monitoring	Major
	Temperature excursion for gadobutrol with risk of freezing	Monitoring	Major criteria2
	IMP management not appropriate	Monitoring	Non major
	Extravasation during gadopiclenol administration	Clinical data base	Major
	Extravasation during gadobutrol administration	Clinical data base	Major criteria2
	Saline flush not done after IMP administration	Monitoring	Non major
Missing data	Age is missing	Clinical data base	Non major
	Sex is missing	Clinical data base	Non major
	Weight is missing	Clinical data base	Non major
	Height is missing	Clinical data base	Non major
	Ethnicity is missing	Clinical data base	Non major
	Race is missing	Clinical data base	Non major

Category	Description	Source	Status
	eGFR measurement at visit 3 or visit 5 is missing	Clinical data base	Non major
	Central Laboratory Biochemistry results not available	Laboratory data base	Non major
	Central Laboratory Hematology results not available	Laboratory data base	Non major
	Vital sign result missing	Clinical data base	Non major
	Tolerance at injection site is not filled in for patient receiving the study product	Clinical data base	Non major
	No Numeric Pain Intensity Scale completed in case of injection site pain	Clinical data base	Non major
Non respect of study's schedule and procedures	MRI examination with gadopiclenol not performed	Clinical data base	Major
	MRI examination with gadobutrol not performed	Clinical data base	Major criteria2
	Time between the two MRI procedures is strictly greater than 14 days and less or equal to 21 days	Clinical data base	Non major
	Time between the two MRI procedures is strictly greater than 28 days	Clinical data base	Major criteria2
	Two different MRI system manufacturer used for both assessments of the same patient	Clinical data base	Non major
	Two different magnetic field strength used for both assessments	Clinical data base	Major criteria2
	MRI machine used not qualified	Monitoring	Non major
	Body region is different between the two MRs	Clinical data base	Non major
	US patients with an indication other than Breast MRI	Clinical data base	Non major
	Physical examination not performed	Clinical data base	Non major
	eGFR method is not the same throughout the trial	Clinical data base	Non major
	eGFR method is not accurate	Clinical data base	Non major
	Time between screening visit and first contrast agent administration is strictly greater than 7 days	Clinical data base	Non major
	Blood sample for central laboratory assessment is not drawn in the time window allowed by protocol	Clinical data base	Non major
	Vital sign is not measured in the time window allowed by protocol	Clinical data base	Non major
	Tolerance at injection site is not measured in the time window allowed by protocol	Clinical data base	Non major
	Last contact is not between 7 and 14 days after the last injection of IMP for patients recruited in France	Clinical data base	Non major
	Deviation in IWRS Process	Monitoring	Non major
	Clinical protocol procedure not respected	Monitoring	Non major
GCP deviation	Deviations related to ICF signature process	Monitoring	Non major
	Source document management not appropriate	Monitoring	Non major

Patients presenting at least one protocol deviation with a status "**Major**" will be excluded from the PPS1 and PPS2.

Patients presenting at least one protocol deviation with a status "**Major criteria1**" will be excluded from the PPS1

Patients presenting at least one protocol deviation with a status "**Major criteria2**" will be excluded from the PPS2

Frequency and percentages of patients with protocol deviations will be presented breaking down by status (major/non major).

Patients with major protocol deviations will be presented by series and globally on the SPS.

- patients with at least one protocol deviation with a status “**Major**”
- patients with at least one protocol deviation with a status “**Major criterial**”,
- patients with at least one protocol deviation with a status “**Major criteria2**”,

Patients with non-major protocol deviations will be presented by series and globally on the SPS as well.

Number of patients in the ARS, extended FAS1, extended FAS2, FAS1, FAS2, PPS1 and PPS2 will be presented by series and overall on Screened Patients Set.

Number of patients in the Safety Set will be presented by contrast agent groups and overall on Screened Patients Set.

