## 2.2. Efficacy criteria

### 2.2.1. Primary criteria

#### **Primary criteria 1: Lesion visualization criteria for gadopiclenol-enhanced MRI compared to unenhanced MRI (off-site read):**

The lesion visualization assessment is based on 3 co-primary criteria: border delineation, internal morphology and degree of contrast enhancement assessed on the images acquired during the MRI performed with gadopiclenol.

Each Independent Blinded Reader (IBR) will record each of the 3 co-primary criteria for up to 3 most representative lesions, on Paired images (contrast-enhanced + unenhanced images) versus Pre contrast images (unenhanced images) on a 4-point scale as described below:

- **Border delineation:**

Delineation of the lesion border is defined as the distinction of lesion from surrounding tissues, structures, or edema; and the detection of extent of the lesion. This criterion will be assessed through the following scale:

- 1 = None: no or unclear delineation
- 2 = Moderate: some areas of clear delineation but also with some significant areas of non-distinct delineation
- 3 = Good: almost clear but not complete delineation
- 4 = Excellent: border outline is sharp with clear and complete delineation

- **Internal morphology:**

Internal morphology of the lesion includes an identification of lesion architecture and the intra-lesion features such as necrosis, hemorrhage and vascularity. This criterion will be assessed through the following scale:

- 1 = Poor: poorly seen
- 2 = Moderate: majority of lesion is poorly seen but with minor parts of lesion visible
- 3 = Good: majority of lesion is clearly seen but with minor parts of lesion invisible
- 4 = Excellent: lesion is well seen and can see “through” lesion to observe any complex areas of necrosis or hemorrhage or cyst formation

- **Degree of contrast enhancement:**

This criterion will be a qualitative assessment (not based on signal intensity measurement) according to the following scale:

- 1 = No: no enhancement
- 2 = Moderate: weakly enhanced
- 3 = Good: clearly enhanced
- 4 = Excellent: clearly and brightly enhanced

The mean score for each of the 3 co-primary criteria of lesion visualization will be calculated as follows:

Mean score = (score of the lesion 1 + score of the lesion 2 (if any) + score of the lesion 3 (if any)) divided by the number of lesions (up to 3 most representative lesions).

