## Primary criteria 2: Lesion visualization criteria for gadopiclenol compared to gadobutrol (off-site read)

The same 3 co-primary criteria of lesion visualization: border delineation, internal morphology and degree of contrast enhancement, will be assessed on the images acquired during the MRI performed with gadopiclenol and those performed with gadobutrol.

The IBR will record each of the 3 co-primary criteria for up to 3 most representative lesions, on Paired images performed with gadopiclenol and Paired images performed with gadobutrol using a 4-point scale. Definitions of each co-primary criteria and score calculation are provided in primary criteria 1 description.

For each reader, only matching lesion on paired images between gadopiclenol and gadobutrol will be considered for the evaluation of the primary criteria 2.

For each reader, if the MR images are not assessable or if no matching lesion on Paired images between gadopiclenol and gadobutrol is identified, then the patient will not be included in the evaluation of primary criteria 2.

The mean score for each co-primary criterion of the lesion visualization will range from 1 to 4.

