#### Non-inferiority of gadopiclenol versus gadobutrol regarding lesion visualization co-primary criteria (primary criteria 2)

CONFIDENTIAL	STATISTICAL ANALYSIS PLAN PHASE III TRIAL GDX-44-011 VERSION NO. 2.0      DATED 25 JANUARY 2021	████████ Page 28 / 57
--------------	---	--------------------------

Each co-primary criterion will be analyzed using a general linear model for each reader independently, modelling the patient's score as a function of the contrast agent group (GBCA: gadopiclenol and gadobutrol) with repeated measures on the patient due to the pairing of contrast agents in patients.

Hence for each off-site reader, the models will be the following:

- Border delineation = contrast agent group + period + error
- Internal morphology = contrast agent group + period + error
- Degree of contrast enhancement = contrast agent group + period + error

The parameters of the general linear model will be estimated using the SAS® procedure Mixed. The procedure used for the non-inferiority analysis will be the following for each co-primary criterion and each off-site reader:

```
proc mixed data = XXX method = REML;
  class subject GBCA period;
  model eval = GBCA period;
  repeated GBCA / subject=subject / type = cs;
/* To get the estimate and the corresponding confidence interval of the paired difference */
  lsmeans GBCA;
  estimate "gadopiclenol - gadobutrol" GBCA 1 -1 /cl;
run;
```

The Student's t-based 95% confidence intervals of the difference between gadopiclenol and gadobutrol will be constructed for each of 3 co-primary criteria using the PPS2 on matching lesions. Results will be presented per off-site reader.

If the lower bound of this confidence interval is above the non-inferiority margin for at least 2 out of 3 readers and for the 3 co-primary criteria, then non-inferiority between gadopiclenol and gadobutrol will be concluded.

As soon as the non-inferiority is demonstrated, the superiority of the gadopiclenol over gadobutrol will be tested using the same method. No adjustment for multiplicity is needed as it is a simple closed testing procedure.

If the lower bound of the Student's t-based 95% confidence intervals of the difference between gadopiclenol and gadobutrol is above 0 for at least 2 out of 3 readers and for the 3 co-primary criteria, then superiority of gadopiclenol over gadobutrol will be concluded.

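### The word *enhancing* in the two not-matching-lesion rows of SAP 5.2 makes membership of the primary non-inferiority set depend on a co-primary outcome, with unknown direction and probably small effect

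*SAP*

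**What the plan says.** SAP 5.2 (Protocol deviations, Imaging category) has two rows on lesions that do not match. The Major criteria2 row covers patients with both examinations available who have no "matching enhancing" "lesions at both examination for all off-site readers". The Major criteria1 row uses the same two words for paired and pre-contrast images with gadopiclenol. Below the table, a patient with a Major criteria2 deviation "will be excluded from the PPS2". SAP 5.6.1 builds the non-inferiority confidence intervals for each of the "3 co-primary criteria using the PPS2 on matching lesions".

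The other definitions carry no enhancement condition. SAP 2.2.1, primary criteria 2: "For each reader, only matching lesion on paired images between gadopiclenol and gadobutrol will be considered for the evaluation of the primary criteria 2". In the data set definitions of SAP 5.2, a patient enters FAS2 when the paired sets from the two agents can be assessed, and the lesion requirement there reads "for at least one matching lesion for at least one off-site reader". The scale for degree of contrast enhancement in SAP 2.2.1 starts at "1 = No: no enhancement".

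**The concern.** Degree of contrast enhancement is one of the three co-primary criteria, and all three must pass for at least two readers. If a lesion was recorded and matched on both paired image sets and scored 1 with one agent, that score is data on the comparison. A rule that uses it to decide who enters the primary set conditions the analysis on its own outcome.

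The row also sits badly with the SAP's own reasons for a per-protocol set. SAP 5.2 defines a deviation as a departure from the design or procedures, and justifies PPS2 by the risk that poor compliance makes the agents look alike. A lesion that does not enhance after a correct injection and scan is a result. Wrong product, volume errors, extravasation and imaging-protocol failures already have their own rows.

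**Working it through.** **1. Trace one patient through the rules.** Assume one lesion, recorded and matched on both paired sets by every reader, and take *enhancing* to mean a score of 2 or more. The SAP does not define the word, so this threshold is an assumption.

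| Gadopiclenol score | Gadobutrol score | Difference | FAS2 | PPS2 as written | Effect of removal on the mean difference |
|---|---|---|---|---|---|
| 1 | 3 | −2 | in | out | moves it up, favours non-inferiority |
| 3 | 1 | +2 | in | out | moves it down, works against |
| 1 | 1 | 0 | in | out | makes a true deficit slightly larger, works against |

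The patient is excluded only if no reader has any matched lesion that enhances on both examinations. With up to three lesions per reader, one such lesion for one reader is enough to stay in.

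**2. Check the sister row.** The Major criteria1 row asks for matching enhancing lesions on paired and pre-contrast images. Enhancement cannot be scored sensibly before contrast. Protocol 7.1.1 says as much when it has readers choose potentially enhancing lesions on the pre-contrast read. The word cannot work there as a score threshold.

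**3. Reproduce the plan's sample size for objective 2.** Inputs from Protocol 11.2: margin 0.35, expected difference 0, SD of the within-patient difference 1.75, two-sided 95% interval, power 80%.

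- Normal approximation: n = (1.960 + 0.842)² × 1.75² / 0.35² = 7.85 × 25 = 196.2, so 197.
- Noncentral t: 199. Power at 200 is 80.4%.
- Enrolment at 33% non-evaluable: 200 / 0.67 = 298.5, so 299, stated as 300.

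The plan's 200 and 300 are confirmed. The point here does not touch them.

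**4. Illustrate the size, in both directions.** The documents give no count of patients whose lesion enhances with only one agent. Assume a net k such patients in 200, each with a 2-point difference on degree of contrast enhancement.

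- Shift in the mean = 2 × k / 200.
- k = 5: 0.05, which is 0.05 / 0.35 = 14% of the margin.
- k = 10: 0.10, which is 29% of the margin.

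Now put the k patients back beside 200 retained patients with mean 0. The shifts are 2 × 5 / 205 = 0.049 and 2 × 10 / 210 = 0.095. With retained SD s, individual difference d (−2 or +2) and new mean μ, the variance is (200s² + 200μ² + k(d − μ)²) / (200 + k). Power for one reader on this one criterion is then:

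| SD of difference | PPS2 as written | Net gadopiclenol failures restored, k = 5 / 10 | Net gadobutrol failures restored, k = 5 / 10 |
|---|---|---|---|
| 1.75 (planning value) | 80% | 69% / 55% | 90% / 95% |
| 1.15 (upper end of the protocol's expected range) | 99% | 95% / 87% | above 99% / above 99% |

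Patients with no enhancement from either agent matter less. If the mean among 200 were −0.10, restoring 10 with a difference of 0 gives −0.10 × 200 / 210 = −0.095.

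**The case against.** The best counter-argument is that *enhancing* is loose wording and the rows mean only that no target lesion matched. Both rows are labelled as not-matching-lesion rows, the trial targets enhancing lesions, and the word makes no sense for pre-contrast images. Redundancy with FAS2 would be no surprise. Deviations are tabulated on all screened patients, and the table also lists a missing gadobutrol MRI as Major criteria2, although such a patient could not be in FAS2 anyway. On that reading nobody extra is removed. This is plausible, but it means the word does no work. Left undefined, it lets two programmers build different PPS2 sets.

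The safeguards are real. Non-inferiority is repeated on FAS2 and again with non-matching lesions on the extended FAS2. Patient and lesion counts are shown for each efficacy dataset, and the final categorization is made and minuted before the blind is broken. A gap between PPS2 and FAS2 would be visible. But the conclusion is drawn from PPS2, and deciding while blinded does not make an outcome-based rule neutral.

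There is also a link to eligibility. Protocol 11.3.3 names, as a major deviation, a patient without a known or suspected enhancing lesion, while the SAP treats failure of any inclusion criterion other than number 6 as non-major. Deleting the word removes the last trace of that example from the major deviations. The mismatch should be reconciled separately. It concerns eligibility on previous imaging, and a post-injection score is not a measure of that.

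**Conclusion.** Followed as written, the rule selects the primary non-inferiority set partly on a co-primary outcome and disagrees with the endpoint and FAS definitions. That is enough to correct it.

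A reader might infer that the rule tilts the trial toward non-inferiority, since gadopiclenol is given at half the molar dose. The documents do not support this. They give no rate of non-enhancement for either agent, the planning assumption is a difference of 0, and the protocol's rationale is that gadopiclenol has at least twice the T1 relaxivity. The rule also removes gadobutrol-only failures and patients with no enhancement from either agent, which works the other way.

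The shift of about 0.05 or 0.10 rests on assumed counts and an assumed 2-point difference. It applies to degree of contrast enhancement only; nothing follows from it for border delineation or internal morphology. The true number is probably small because all readers must agree.

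**What to change.** Delete *enhancing* from both rows so that they refer to no matching lesion, in agreement with SAP 2.2.1 and the FAS1 and FAS2 definitions. Patients with a matched lesion that does not enhance then stay in PPS1 and PPS2 with their recorded scores, unless another major deviation applies.

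The cost is one word in each of two rows, with no new data or model. PPS2 may gain a few patients. Some may have lesions that enhance with neither agent, and these add differences near zero on that criterion, so report their number beside the result.

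The change does not recover every case. Protocol 7.1.1 has readers prioritize enhancing lesions on paired images, so a lesion that fails to enhance with one agent may never be recorded or matched, and is then missing from FAS2 as well.
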